Specific Aim 3: Investigate the extent to which tDCS modifies resting state network segregation.

Hypothesis 3: Compared to the sham tDCS group, the active tDCS group will demonstrate improved segregation of resting state networks at post-training relative to baseline.

[figure not shown]
6. Research Plan:

Study Overview

Screening	Baseline	Locomotor Learning	Post (1 Day)	Post (1 Week)	Post (1 Month)
1 Visit	1-2 Visits	4 Visits	1 Visit	1-2 Visits	1 Visit

 • Informed Consent • Cognitive Function • Walking Function 	
 • Obstacle walking with fNIRS • Cognitive Function • MRI: 
 › Structural › Resting state › Task-based (imagined obstacle walking) • Blood Draw 	
 • Active or sham tDCS during: • Obstacle task practice 
 1 - blocked practice 2 - variable practice 3 - combined practice 4 - full task practice 	
 • Obstacle walking with fNIRS 	
 • Obstacle walking with fNIRS • Cognitive Function • MRI: 
 › Structural › Resting state › Task-based (imagined obstacle walking) • Blood Draw 	
 • Obstacle walking with fNIRS • Cognitive Function

Up to one hundred older men and women will be enrolled in the intervention component of this study. An additional 15 participants (estimated) may enroll in the intervention but discontinue participation before completing the protocol. A larger number (up to 400) may participate in screening by telephone and/or onsite, but will fail the screening tests and not proceed to the study intervention. Participants will undergo the following sequence of events:

- *Telephone Screening*: Participants will be screened by telephone to determine if they meet basic enrollment criteria including age and general health status. If patients authorized us to view their medical records, those records may be examined to verify absence of exclusion diagnoses, to obtain complete/accurate medication lists, and to assess whether participants have successfully completed prior MRI scans.

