- *Informed Consent and Onsite Screening Visit*: Participants who pass the phone screen will be invited to participate in on-site screening. Informed consent will be obtained. Mobility function, cognitive function, and health/safety screening will be conducted. This single visit will last approximately 3.5 hours. Qualifying participants will be invited to participate in the full study with or without MRI.
- *Baseline* Participants will undergo a test of walking over obstacles, turning while walking (90 degree turns and 180 degree turns), turning while standing in place (360 degree turn), cognitive function, blood draw, and MRI scans at the UF McKnight Brain Institute (structural, functional, and resting state MRI scans) if MRI screening passed. Baseline assessment will last about 4 hours and may be completed over 1 or 2 visits based on scheduling flexibility of the participant, study personnel, and equipment.
- *Study Intervention Visits*: Participants will attend four intervention sessions in which they will practice a “locomotor learning” task comprised of a 10m walking course with obstacles and transitions between hard and soft floor surfaces. During this task they will receive either active or sham transcranial

The obstacles walking task includes a series of foam obstacles and foam mats. This walking task is used for baseline visits, study intervention visits, and post visits.

direct current stimulation (tDCS) to the frontal portion of the brain. Each visit will last approximately one hour.

- **1-Day Post Assessment:** Participants will undergo a test of walking over obstacles.
- **1-Week Post Assessment:** Participants will undergo a test of walking over obstacles, cognitive function assessment, blood draw, and MRI scans (MRI eligible participants only) at the UF McKnight Brain Institute (structural, functional, and resting state MRI scans). Post assessments will last about 4 hours and may be completed over 1 or 2 visits based on scheduling flexibility of the participant, study personnel, and equipment.
- **Visit 9: 1-Month Post Assessment:** Participants will undergo a test of walking over obstacles, turning tasks, and cognitive function assessment. This visit will last approximately 2 hours.

Telephone Screening

Participants will be screened by telephone to determine if they meet the following criteria:

Inclusion criteria

- Age 65 - 95 years

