- Visuospatial working memory –remember the sequence and location of items that appear and disappear from the screen.

Locomotor Learning Visits

Description of Locomotor Learning Task

Each of the four locomotor learning sessions will include 20 minutes of actual task practice. Short rest breaks are built in throughout this period, and participants will also be allowed to take additional rest breaks as often as they wish. Participants will wear a gait belt around their waist during this task, which allows research staff to more easily grip and assist a participant if he/she becomes unsteady. The sessions will be scheduled approximately equally over two weeks. To optimize learning and retention, we will use a tiered approach for task practice which includes blocked practice for Session 1, random practice for Session 2, combined practice for Session 3, and full course practice for Session 4. Blocked practice means that one isolated component of the task (e.g., transitioning between soft and hard surfaces) will be practiced before moving onto another isolated component (e.g., stepping over single obstacles), and then another (e.g., stepping over double-height obstacles). Random practice means that the aforementioned isolated components will each be practiced multiple times, but interspersed in a random order. Combined practice means that the components will no longer be practiced in isolation, but rather will be combined such as stepping over and obstacle during the transition between soft and hard surfaces. Full course practice means that the participant will practice on the actual course that is used for assessment, at both slower and fast speeds. This tiered approach to learning ensures that participants attain full understanding and mastery of each component early on. As mastery of the basic components is achieved, the complexity and attentional demands of the task are increased to promote robust learning and offline consolidation.

tDCS during Locomotor Learning

Participants will be randomized to receive either active or sham tDCS, which will be delivered simultaneously during the locomotor learning task. A commercially available tDCS unit (Soterix Medical Inc.) will be used for delivery of stimulation. The unit will be carried inside of a backpack so that stimulation can be delivered during walking. The tDCS unit is very lightweight, so wearing it in a backpack adds no appreciable effort to the walking tasks.

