For Specific Aim 1 we seek to determine whether active tDCS is superior to sham tDCS for enhancing retention of locomotor learning after one week. The primary outcome is the change in walking speed on the obstacle course between the end of the learning period to the one week post visit. We are powering the study to detect group differences in retention of walking performance. We will use an ANOVA model to test group differences, and will account for demographic covariates. To estimate sample size for this aim, we have conducted a pilot study with 12 older adult participants who were randomized to an active (n=5) or sham (n=7) tDCS group. To assess retention, the mean walking speed from the final three trials of the learning session were compared to the mean walking speed from the three retention trials measured one week later. The active tDCS group showed a between-session gain in walking speed of nearly 0.07 m/s. The sham tDCS group showed a drop in between-session speed of approximately -0.04 m/s. This between group-difference of 0.1 m/s is considered clinically meaningful and had a large effect size of 0.87. The whole-group standard deviation of response was 0.12. Based on these preliminary data, we will need 48 participants (n=24 per group) to detect a statistically significant group difference at alpha=0.05 and beta=0.20 (i.e., 80% power). To be conservative, we will enroll 60 participants to account for potential dropout and to ensure sufficient statistical power.

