For Specific Aim 2 we seek to determine if several key measures of brain integrity/function help to explain individual differences in the retention of locomotor learning after one week. We will use multivariate regression models that account for demographic covariates. Based on the assumptions of univariate linear regression, a sample size of 60 with alpha=0.05 and beta=0.20 (i.e., 80% power) will allow us to significantly detect correlations coefficients as small as 0.355. Values below this level are generally considered very weak, and thus there would be little benefit to powering the study to detect smaller values. Based on our pilot data and findings from the literature, we are very likely to observe stronger associations that will achieve statistical significance. For instance, our pilot data show that working memory performance and prefrontal activation are associated with visuomotor learning with correlations of 0.57 and 0.48, respectively. Our pilot data also show that resting state default mode network connectivity is associated with retention of learning with a correlation of 0.46. Our statistical models will account for a number of demographic and other covariates, thereby accounting for some of the variability in the data set and improving our ability to detect these mechanism-related associations.

For Specific Aim 3 we seek to acquire evidence that tDCS modifies resting state network connectivity and segregation during motor learning. Prior studies have shown that even a single session of motor learning or a single session of tDCS can modify the connectivity of resting state brain networks. However, this remains an exploratory aim and we have not specifically powered the study for this purpose. Nevertheless, as with the other measures described above, if the effect size is moderate or large we are likely to detect it with statistical significance.

Data and Safety Monitoring Plan

Adverse Event Reporting

Adverse events will be reported according to the guidelines of the University of Florida Institutional Review.

Reporting within 5 days of the PI becoming aware will apply to adverse events that meet all of the following criteria:

- Serious
- Unexpected
- Related or the Relationship is “more likely than not”

Adverse events will be added to the cumulative event table and reported at continuing review when they meet either of the following criteria:

- Serious (but expected) and related or the relationship is “more likely than not”.

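### Should the Aim 1 analysis also adjust for obstacle-course speed before training?

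*Combined protocol and SAP*

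**What the plan says.** Section 10 defines the primary outcome as the "change in walking speed on the obstacle course between the end of the learning period to the one week post visit". For the test it says: "We will use an ANOVA model to test group differences, and will account for demographic covariates". The demographic covariates are not listed.

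Section 6 (Research Plan) shows that a pre-training measurement exists. The Baseline column of the Study Overview table includes "Obstacle walking with fNIRS", and the text beside the description of the intervention visits adds: "This walking task is used for baseline visits, study intervention visits, and post visits". Stimulation is given only during the learning sessions, after baseline.

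The only mention of covariates beyond demographics is in the Specific Aim 2 paragraph of Section 10: "Our statistical models will account for a number of demographic and other covariates". It names no variable and concerns the associations with brain measures. It is not relied on here as covering Aim 1.

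**The concern.** Adjusting for the baseline value of the outcome is usually one of the safest ways to gain precision in a randomised trial. Here the task is measured before randomised treatment starts, it is the task on which the outcome is scored, and it needs no extra visit. The arms are small (24 needed, 30 planned), so a strong covariate could matter. If the choice is not fixed in advance, adding the covariate after the data are seen would be post hoc. At stake would be some power in the primary test and some protection against a chance difference in walking ability between the arms.

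**Working it through.** **Inputs.** From Section 10: difference 0.10 m/s, SD of the change 0.12 m/s, alpha 0.05 (taken as two-sided), 24 per arm required and 60 enrolled (30 per arm). Assumed, because the documents do not give them: three demographic covariates unrelated to the outcome, and rho, the correlation of pre-training speed with the retention change after the demographics.

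**1. The plan's own figure.** The standardised difference is 0.10/0.12 = 0.833. A two-sided t-test at 80% power needs 23.6 per arm, so 24 per arm and 48 in total, as stated. Power at 24 per arm is 80.7%, and at 30 per arm 88.8%. The stated size takes no credit for any covariate.

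**2. Why the usual argument does not carry over.** The outcome is one-week speed minus end-of-learning speed. With equal SDs,

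rho = [corr(pre, 1 week) - corr(pre, end)] / sqrt(2 x (1 - corr(end, 1 week))).

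However strongly pre-training speed predicts later speed, rho is zero if it predicts both later speeds equally well. For example, with correlations of 0.70 and 0.75 and an end-to-one-week correlation of 0.80, rho = 0.05/sqrt(0.40) = 0.08.

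**3. What the covariate costs and returns.** With c covariates and N analysed, degrees of freedom are N - 2 - c, the average variance inflation is 1 + c/(N - c - 3), and the residual SD is 0.12 x sqrt(1 - rho^2). At N = 48:

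- c = 3: inflation 1 + 3/42 = 1.071, 43 degrees of freedom.
- c = 4: inflation 1 + 4/41 = 1.098, 42 degrees of freedom.

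Power from the noncentral t distribution:

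| Per arm | Demographics only | + pre-training speed, rho 0 | 0.15 | 0.2 | 0.3 | 0.4 | Break-even rho |
|---|---|---|---|---|---|---|---|
| 24 | 77.8% | 76.8% | 77.7% | 78.5% | 80.6% | 83.6% | 0.158 |
| 30 | 87.0% | 86.4% | 87.1% | 87.7% | 89.3% | 91.5% | 0.138 |

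At 24 per arm and an end-to-one-week correlation of 0.80, break-even requires the two pre-training correlations to differ by 0.158 x sqrt(0.40) = 0.10.

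**4. Weighing gains against losses.** Take a grid with both pre-training correlations from 0.6 to 0.8 and the end-to-one-week correlation from 0.7 to 0.9, 21 points each. Median |rho| is 0.10; 18% of cases reach 0.2, 3% reach 0.3 and 0.2% reach 0.4. The net change in power from adding pre-training speed to three demographics is:

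| Per arm | Mean | Median | Share of cases in which power falls |
|---|---|---|---|
| 24 | -0.18 points | -0.62 points | 71% |
| 30 | +0.04 points | -0.31 points | 65% |

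With no other covariate in the model the means are -0.11 and +0.06 points, so the answer does not depend on the assumed three demographics.

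**5. The edges.** If rho is 0 and the arms differ by chance on pre-training speed at the 95th percentile of absolute imbalance, adjusting for that speed alone lowers power from 80.7% to 77.3% at 24 per arm and from 88.8% to 86.6% at 30. At 50 per arm (Section 6 allows up to 100 participants), power is 98.5% unadjusted and 98.4% to 99.0% with pre-training speed alone for rho from 0 to 0.3.

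**The case for a change.** The best case for adding the covariate has four parts.

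- **Upside.** If rho were 0.3, power would rise by 80.6 - 77.8 = 2.8 points before rounding differences (2.7 unrounded) at 24 per arm. The average loss at rho 0 is only about 1.0 point. The grid is assumed and treats the two pre-training correlations symmetrically, so it is not evidence about this trial. All of that is fair. But an unknown rho supports inclusion no better than omission, and nothing in the documents points to a value above break-even.
- **Prognosis.** The sponsor expects baseline brain and cognitive measures to predict retention (Hypotheses 2a and 2c), and Section 10 gives a pilot correlation of 0.46 between a resting-state network measure and retention. Those are not walking speed and do not give rho.
- **Chance imbalance.** With small arms, adjustment would correct a chance difference in pre-training speed. It does so usefully only if that speed predicts the retention change, which is the same unsupported premise. Randomisation already makes the unadjusted comparison valid.
- **Prespecification.** Section 10 leaves the demographic covariates unlisted. That is true, but it is missing detail that would remain whatever is decided about pre-training speed. The plan does not propose to add pre-training speed later, nor to adjust for end-of-learning or one-day speed, so there is no post hoc step or post-treatment adjustment to correct.

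**Conclusion.** The concern does not hold. The Aim 1 model is valid as written, and its 48 participants reproduce from the stated difference and SD. Because the outcome is a change between two times after training has begun, pre-training speed is not the baseline of that change, and the usual argument for baseline adjustment does not apply. On the assumed range of correlations the expected effect of adding it is close to zero (-0.18 points of power at 24 per arm, +0.04 at 30), with a small loss as the typical result. A statistician could include it or leave it out.

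The size of this result rests on the assumed grid and on three demographic covariates. The main conclusion needs only the outcome's definition and the absence of any stated reason to expect rho above about 0.14 to 0.16. Evidence of a clearly larger rho would make inclusion worthwhile, but omission would still not be an error.

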Electrode preparation will involve saturating a sponge electrode with exactly 10cc of 0.9% saline solution using marked syringe (5cc/side). Electrodes will be placed using lightweight plastic “headgear” that is adjustable for head size and can hold the electrode montage in place during stimulation. We have considerable experience delivering this exact tDCS protocol during walking in our ongoing research studies.

Active tDCS: Twenty minutes of 2.0mA direct current through two biocarbon rubber electrodes encased in saline soaked 5cm² sponges placed over the frontal cortices at F3 and F4 (based on the international “10-20 system” of standardized brain electrode placement). 2.0mA was chosen based on prior research.

Sham tDCS: Sham stimulation is performed with the same device and all procedures will be identical except for the duration of stimulation. Participants will receive 30 seconds of 2.0mA of direct current stimulation at the beginning of each rehabilitation session. Since participants habituate to the sensation of tDCS within 30-60 seconds of stimulation, this procedure provides the same sensation of active tDCS.

Post Visits

Participants will return to lab approximately 1 day, 1 week, and 1 month after completing the locomotor learning protocol. These visits will be very similar to the baseline visit, including each of the components listed above in that section. At each visit they will walk over the obstacle course again to assess changes in performance. At the 1 week and 1 month visits the cognitive function assessment will be repeated. At the 1 week post visit the MRI protocol and/or blood draw protocol will be repeated (except for the 2.5ml PaxGene, which is only needed at baseline) depending on MRI eligibility.

Possible Discomforts and Risks:

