tDCS Safety: Our protocol uses stimulation parameters that are considered standard practice, and have been used safely in prior research. The most common side effects of tDCS are slight itching, tingling, and reddening of the skin under the electrode. Participants typically habituate to itching or tingling sensations within 60 seconds of stimulation. To minimize risk associated with tDCS, participants will be monitored throughout stimulation sessions and asked to report any discomfort. If stimulation sensation is uncomfortable, the stimulation levels will be decreased to a comfortable level or will be stopped.

fNIRS Safety: fNIRS poses no safety risk. Infrared light from the fNIRS device is not harmful and elicits no sensation. Sensors may be secured to the skin using adhesive tape, which could lead to mild skin irritation in those who are sensitive to adhesives. If a person indicates or displays such a sensitivity, we will avoid using adhesive tape and instead use elastic fabric or straps to secure the sensors.

Questionnaire administration: Questionnaire data are collected in secure spaces where the interview cannot be overheard. Participants will be informed that they are not required to answer questions that they do not wish to answer.

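### The primary ANOVA uses one change score and so drops anyone without a 1-week value, although a repeated-measures model on visits already scheduled would guard against part of the bias this can cause

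*Combined protocol and SAP*

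**What the plan says.** Section 10 (Specific Aim 1) defines the outcome: "The primary outcome is the change in walking speed on the obstacle course between the end of the learning period to the one week post". The test is given in one sentence: "We will use an ANOVA model to test group differences, and will account for demographic covariates". No analysis set, missing-data method or sensitivity analysis is named anywhere in the document.

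The same obstacle course is walked more often than this model uses. Section 6 (Post Visits) states: "Participants will return to lab approximately 1 day, 1 week, and 1 month after completing the locomotor learning protocol", with the course walked each time, and the course is also walked at baseline. Hypothesis 1 in section 5 covers 1 month as well as 1 week, but section 10 gives no model for 1 month.

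Loss is expected, and the counts differ. Section 10 needs 48 participants and enrols 60 to allow for dropout. Section 6 (Study Overview) has up to 100 in the intervention and adds: "An additional 15 participants (estimated) may enroll in the intervention but discontinue participation before completing the protocol".

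The tDCS Safety paragraph says that if stimulation is uncomfortable "the stimulation levels will be decreased to a comfortable level or will be stopped". The plan does not say how such participants are analysed.

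**The concern.** A change-score ANOVA leaves out anyone who lacks either value. The 1-week assessment is demanding: about 4 hours over one or two visits, with cognitive tests, a blood draw and, for eligible participants, MRI. The table in section 6 lists only the obstacle walk at 1 day. It is therefore plausible that some people finish learning, attend at 1 day and then miss 1 week.

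If those people differ in performance from those who return, and the pattern differs by arm, the comparison is no longer between the groups as randomised. Their 1-day speed would show part of that difference, and the stated model discards it. Enrolling 60 to end with 48 protects power; it does nothing about this bias.

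**Working it through.** **1. The plan's own figure.** Section 10 gives a difference of 0.10 m/s, an SD of 0.12 m/s, alpha 0.05 and 80% power. A two-sided two-sample t-test at 0.10/0.12 = 0.83 needs 23.6 per arm, so 24 per arm and 48 in all, as stated. (The quoted effect size of 0.87 would give 22 per arm, so 0.10 and 0.12 are used below.)

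**2. Implied loss.**
- Section 10: 1 − 48/60 = 20%.
- Section 6: 15/(100 + 15) = 13.0%. At that rate 48 evaluable needs 48/0.870 = 55.2, so 56.

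**3. Bias among those with a 1-week value.** The following are assumptions, not in the documents:
- SD 0.12 m/s for both the 1-day and the 1-week change, with correlation ρ of 0.5 or 0.7.
- In each arm, the people lost before 1 week are those lowest on their 1-day change plus random noise of SD 0.06.

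The selection score has SD √(0.12² + 0.06²) = 0.134, so its correlation with the 1-week change is ρ × 0.12/0.134 = 0.894ρ. If a fraction p is lost from the bottom, the mean standardised score of those who remain is m(p) = φ(z_p)/(1 − p):
- m(0.20) = 0.2800/0.80 = 0.350
- m(0.10) = 0.1755/0.90 = 0.195
- m(0) = 0

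Bias in the arm difference = 0.12 × 0.894ρ × [m(active) − m(sham)].

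| Loss, active v sham | ρ = 0.5 | ρ = 0.7 |
|---|---|---|
| 20% v 10% | 0.12 × 0.447 × 0.155 = +0.008 | 0.12 × 0.626 × 0.155 = +0.012 |
| 20% v 0% | 0.12 × 0.447 × 0.350 = +0.019 | 0.12 × 0.626 × 0.350 = +0.026 |
| equal | 0 | 0 |

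Simulation with 30 per arm agrees to within about 0.002 m/s. The sign is positive because the heavier loss was placed in the active arm; placed in the sham arm, it reverses.

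**4. What the 1-day value recovers.** A likelihood analysis of the 1-day and 1-week changes together was compared with the same completers.
- Every lost person has a 1-day value: bias of about 0.001 m/s or less, with almost the same standard error (0.0334 v 0.0335 at 20% v 10%, ρ = 0.7).
- Half have one: at 20% loss the mean score of people with any data is (0.280 − 0.140)/0.90 = 0.156. For 20% v 0%, 0.156/0.350 = 44% of the bias remains, or +0.008 to +0.012 m/s.
- None has one: nothing is removed.

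**5. A second mechanism.** Assume 20% v 6% loss, correlation 0.6, and odds of loss multiplied by e for each SD of worse change.

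| Loss depends on | Completers | With 1-day values for all |
|---|---|---|
| nothing related to outcome | 0.000 | 0.000 |
| the 1-day change | +0.009 | 0.000 |
| the unseen 1-week change | +0.014 | +0.009 |

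These checks used two changes. They did not include baseline or 1-month speed, so they show the principle and not the exact gain from the full model proposed below.

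**The case against.** Four stronger readings are tempting, and the documents do not support them.

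- **That discontinuers are excluded and replaced by rule.** The sentence on 15 additional participants is a recruitment headcount. Section 10 puts dropout inside the 60. Restriction to people with both values follows from the model; it is not a stated exclusion.
- **That uneven dropout alone biases the result.** It does not. At 20% v 6% unrelated to outcome, the bias is zero.
- **That active current will drive people out.** Possible Discomforts and Risks reports no difference between active and sham in adverse-effect frequency across 209 studies. Sham also begins at 2.0 mA, and the sensation is said to fade within about a minute. Reducing or stopping current is not the same as leaving follow-up.
- **That later visits would correct for people who stop through discomfort.** Stimulation is given only in the four learning visits. Someone who quits then has no end-of-learning value and normally no 1-day value, so nothing is recovered.

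It is also fair to say that the dropout split, correlation and strength of selection are all assumed. At 20% v 10% the bias is only 0.008/0.0335 to 0.012/0.0335, or about a quarter to a third of a standard error. About a quarter of the target effect is reached only when all loss falls in one arm and mostly among its worst performers.

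What stands is that the stated model discards relevant data that the trial will already hold, and leaves the primary result open to a bias that can be partly prevented at little cost.

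**Conclusion.** The concern holds in a limited form. The single-change ANOVA uses only people with both an end-of-learning and a 1-week value. If people who finish learning miss 1 week unevenly by arm and in relation to performance, the arm difference shifts by about 0.01 m/s (20% v 10%) to 0.026 m/s (20% v 0%), or roughly 8% to 26% of the 0.1 m/s target. The shift is zero if loss is unrelated to outcome, or equal in rate and in its relation to outcome in both arms. A likelihood model removes it when the lost people have a 1-day value and missingness depends on what was observed. It removes slightly more than half when half of them do, and none when none do. Nothing in the documents shows that such loss will occur. The change is worth making because it is cheap, and it would also supply the missing 1-month analysis.

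**What to change.** In section 10:

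1. Make the primary analysis a likelihood-based repeated-measures model of obstacle-course speed at end of learning, 1 day, 1 week and 1 month, with arm-by-visit and baseline-speed-by-visit terms and the planned demographic covariates. Baseline needs its by-visit term: with one coefficient for all visits it cancels from a change between visits.
2. Keep the primary contrast as the arm difference in change from end of learning to 1 week. Take the 1-month contrast of Hypothesis 1 from the same model.
3. Include every randomised participant with any of these post-training values, in the assigned arm, whether or not stimulation was reduced or stopped.
4. Report losses by arm and by time, separating those before and after the end of learning.
5. Add a sensitivity analysis for data not missing at random, since the model cannot recover people who leave before the end of learning or whose absence depends on the unseen 1-week value.
6. Reconcile the enrolment and dropout counts in sections 6 and 10.

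The cost is SAP wording, a somewhat more complex model, and reliance on a missing-at-random assumption and a covariance structure. No visits or participants are added.
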